10.1.1. Response in VHL Disease-Associated ccRCC Tumors

Anti-tumor activity will be assessed by non contrast or contrast computerized tomography (CT) or magnetic resonance imaging (MRI) at baseline, within 7 days before the Week 13 visit and every 12 weeks thereafter. Patients will be imaged using the same technique at baseline and each follow up assessment.

Response assessments will be made using RECIST 1.1 (Appendix 3), modified to follow ccRCC tumors only. Best confirmed response and PFS will be determined for all patients. DOR and TTR will be determined for all patients with a best confirmed response of PR or CR. The ORR for VHL disease-associated ccRCC tumors will be determined.

10.1.1.1. Response in VHL Disease-Associated Tumors

Best confirmed response rate, PFS, DOR, and TTR for tumors associated with VHL disease in other (non-renal) organ systems (pancreas or adrenal gland, or hemangioblastomas or retinal angiomas) will be evaluated by modifying RECIST 1.1 criteria. Tumors will be assessed in individual organ systems independently (Appendix 4). The ORR for each of the other VHL disease-associated non-ccRCC tumors will be determined.

10.1.2. Pharmacodynamics and Biomarker Assessments

Blood samples for analysis of PD effects (biomarkers) will be obtained at the Week 1, Day 1 visit before and 6 hours after study drug administration. Pharmacodynamic biomarkers to be assessed may include, but are not limited to, levels of EPO and VEGFA. Whole blood samples will be collected for single nucleotide polymorphism analyses of genes (231) encoding proteins that may be involved in the transport or metabolism of PT2385.

Details for the collection, processing, storage, and shipment of samples for the determination of PD effects can be found in the study laboratory manual.

10.1.2.1. Tissue Sample Collection

Archival tumor tissue samples will be obtained whenever possible from all patients. Additionally, fresh tissue samples will be obtained from consenting patients in whom tumor tissue is accessible (patients who undergo tumor excision during the study). Tumor tissue samples will be analyzed for HIF-2 α and HIF-1 α expression by immunohistochemistry..

Tumor tissue samples may be subjected to mRNA analyses for the expression of HIF-1 α , HIF-2 α and target genes that have been found in preclinical studies to be associated with the sensitivity of ccRCC tumors to HIF-2 α antagonism (Chen et al, 2016). Genomic DNA from tumor tissues may also be analyzed to confirm the loss of heterozygozity of *VHL*, and to assess the status of genes, such as *PBRM1*, *BAP1*, *TP53*, *SETD2*, and *TCEB1*, that have been found to be altered in ccRCC (Sato et al, 2013). Data from these analyses will be used retrospectively to evaluate their utility as predictors of clinical benefit from treatment with PT2385.

Details for the collection, processing, storage and shipment of tissue samples can be found in the study laboratory manual.

11. PHARMACOKINETIC ASSESSMENTS

Blood samples for the determination of plasma concentrations of PT2385 and its primary metabolite PT2639 will be collected at the Week 1, Day 1 visit before and 6 hours after study drug administration and at the Week 3, Week 5 and every 4 weeks through the Week 17 visits before study drug administration (Schedule of Events, Appendix 1). The date and time of collection of all PK blood samples should be recorded.

Validated liquid chromatography/mass spectrometry methods will be used to assay the samples for plasma concentrations of PT2385 and PT2639. Additional metabolites, if detected, may be assessed using non-validated methods. Details for the collection, processing, storage, and shipment of samples can be found in the study laboratory manual.

12. ASSESSMENT OF SAFETY

12.1. Safety Assessments

Safety assessments include the following:

- Physical examinations
- Vital sign measurements (including pulse oximetry)
- 12-lead electrocardiograms (ECG) with QTc interval determination
- Clinical laboratory measurements
- Concomitant medications
- Incidence, intensity, and relationship of AEs and serious adverse events (SAEs)
- Effects on fertility in males (orchidometry, semen analysis, and measurement of testosterone, follicle-stimulating hormone, luteinizing hormone, and inhibin B levels)

Safety and tolerability will be determined by symptoms, signs, and abnormal laboratory test results. The Investigator will monitor the laboratory test findings. Abnormalities of laboratory test results may or may not, in the opinion of the Investigator, be considered clinically significant. All clinically significant abnormal laboratory test results will be reported on the Adverse Event CRF and will be followed until a return to normal or baseline levels. Abnormal laboratory test result that is abnormal during the course of the study but not considered clinically significant will be followed at the discretion of the Investigator.

12.1.1. Demographic/Medical History

Demographic data include gender, age, race, and ethnicity, and will be collected during the time period indicated for Screening in Appendix 1. Medical and surgical history will be recorded during Screening and will include documentation of the date/year of VHL diagnosis, documentation of prior therapies for VHL and documentation of all currently active and relevant medical and surgical conditions.

12.1.2. Eastern Cooperative Oncology Group Status

Eastern Cooperative Oncology Group (ECOG) Status performance status will be assessed using the grading system shown in Appendix 2, at the time points indicated in Appendix 1.

12.1.3. Vital Signs

Vital signs (blood pressure, pulse, respirations, pulse oximetry and temperature) will be assessed as noted in Appendix 1. All blood pressure measurements should be taken after the patient has rested in a seated position for at least 3 minutes.

Monitoring of oxygen saturation

Oxygen saturation should be measured by pulse oximetry at each visit and at any time a patient presents with any new or worsening respiratory symptoms. Readings at rest and on exertion should be obtained at each time point. The extent of the exertion should be based on the judgment of the Investigator, but should remain consistent for each individual patient throughout the study. If the patient's status changes, the Investigator can alter the extent of exertion based on their medical judgment. If a patient shows changes on pulse oximetry (oxygen saturation < 92%) or other pulmonary disease related signs (e.g., hypoxia, fever) or symptoms (e.g., dyspnea, cough, fever) consistent, the patient should be immediately evaluated to rule out pulmonary toxicity. Evaluation may include chest x-ray, arterial blood gas analysis, pulmonary function testing including diffusion capacity, and co-oximetry as well as evaluations for specific causes of hypoxia/dyspnea, such as CT scan, CT angiogram or ventilation-perfusion scan.

12.1.4. Weight and Height

Weight will be measured and recorded at each study visit according to the Schedule of Events (Appendix 1). Height will be assessed during Screening only.

12.1.5. Physical Examination

The physical examination will include evaluation of the head, eyes, ears, nose, and throat (HEENT), cardiovascular, dermatological, musculoskeletal, respiratory, gastrointestinal, and neurological systems. Physical examinations should be performed according to the Schedule of Events (Appendix 1). Funduscopic exams must be performed at Screening, Baseline, and every 12 weeks during the treatment period. Before administration of the first dose of study drug, any new or worsened abnormalities (other than those due to protocol required procedures) should be recorded as medical history. After the initiation of study drug administration, any clinically significant new or worsened abnormalities noted on the physical examination will be recorded as AEs. No rectal or pelvic examination is required.

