12.2. Adverse and Serious Adverse Events

12.2.1. Definition of Adverse Events

12.2.1.1. Adverse Events

An AE is defined as any untoward medical occurrence in a patient regardless of its causal relationship to study treatment. An AE can be any unfavorable and unintended sign (including any clinically significant abnormal laboratory test result), symptom, or disease temporally associated with the use of the study drug, whether or not it is considered to be study drug related. Included in this definition are any newly occurring events and any previous condition that has increased in severity or frequency since the administration of study drug. Disease progression is a study endpoint and consequently, should not be reported as an AE. However, if a patient dies from disease progression with no other immediate causes, "disease progression" should be reported as an SAE (Section 12.7).

All AEs that are observed or reported by the patient during the study (from the time of administration of the first dose of study drug until the final visit indicated in Appendix 1) must be reported, regardless of their relationship to study drug or their clinical significance.

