12.2.1.2. Serious Adverse Events

An SAE is any AE occurring at any dose and regardless of causality that meets any of the following criteria.

- Results in death
- Is life-threatening
- Requires inpatient hospitalization > 24 hours or prolongation of existing hospitalization
- Results in persistent or significant incapacity or substantial disruption of the ability to conduct normal life functions
- Is a congenital anomaly or birth defect in an offspring of a patient taking study drug
- Is an important medical event

The term "life-threatening" refers to an event in which the patient is at immediate risk of death at the time of the event. The term does not refer to an event that hypothetically might cause death if it were more severe.

Important medical events are those that may not meet any of the criteria defined above; however, they may be considered serious when, based upon appropriate medical judgment, they may jeopardize the patient and may require medical or surgical intervention to prevent one of the other outcomes listed in the SAE definition.

Pregnancy is not considered an AE; however, information will be collected for any pregnancies that occur during the study (from the time the first dose of study drug is administered until the final visit indicated in Appendix 1). Certain pregnancy outcomes will require submission as an SAE.

The Investigator is responsible for reporting to Peloton Therapeutics or designee all AEs and SAEs that are observed or reported by the patient during the study (from the time the first dose of study drug is administered until the final visit indicated in Appendix 1), regardless of their relationship to study drug or their clinical significance. All SAEs reported or observed during the study must be followed to resolution or until the Investigator deems the event to be chronic or the patient to be stable. Peloton Therapeutics or designee may contact the Investigator to obtain additional information on any SAE that has not resolved at the time the patient completes the study.

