12.6. Recording Adverse Events

All conditions present before administration of the first dose of study drug should be documented as medical history. All drug-related (possible or probable, see Section 12.4) AEs and abnormal laboratory test results reported or observed during the study must be followed to resolution (either return to baseline or within normal limits). All other AEs will be followed through the final visit indicated in Appendix 1. Information to be collected includes type of event, date of onset, date of resolution, Investigator-specified assessment of severity and relationship to study drug, seriousness, as well as any action taken.

While an AE is ongoing, changes in the severity (e.g., worsening and improving) should be noted in the source documents but, when documenting the AE, only the total duration and greatest severity should be recorded in the CRF. AEs characterized as intermittent require documentation of onset and duration.

AEs resulting from concurrent illnesses, reactions to concurrent illnesses, reactions to concurrent medications, or progression of disease states must also be reported. Preexisting conditions (present before the start of the AE collection period) are considered concurrent medical conditions and should NOT be recorded as AEs. However, if the patient experiences a worsening or complication of such a concurrent condition, the worsening or complication (except disease progression) should be recorded as an AE. Investigators should ensure that the AE term recorded captures the change in the condition (e.g., "worsening of...").

Each AE should be recorded to represent a single diagnosis. Accompanying signs (including abnormal laboratory test values or ECG findings) or symptoms should NOT be recorded as additional AEs. If a diagnosis is unknown, sign(s) or symptom(s) should be recorded as an AE(s). Changes in laboratory test values or ECG parameters are only considered to be AEs if they are judged to be clinically significant (i.e., if some action or intervention is required or if the Investigator judges the change to be beyond the range of normal physiologic fluctuation). If abnormal laboratory test values or ECG findings are the result of pathology for which there is an overall diagnosis (e.g., increased creatinine levels in renal failure), only the diagnosis should be reported as an AE.

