13.3.6.1. Adverse Events

Adverse events occurring from the time the patient gives consent but prior to study drug administration will be captured on the Medical History CRF. All AEs occurring on or after the first day of treatment and within 30 days after administration of the last dose of study drug will be considered to be a treatment-emergent adverse event (TEAE).

08LO5Z

Adverse events will be coded according to the latest Version of the Medical Dictionary for Regulatory Activities (MedDRA). The severity of AEs will be coded according to NCI CTCAE 4.03. Treatment-related AEs are AEs that are not stated as unrelated to PT2385.

An overall summary of TEAEs will summarize the number (%) of patients with at least 1 of the following.

- TEAE
- PT2385 related TEAE
- Grade 3 or higher TEAE
- Grade 3 or higher PT2385 related TEAE
- Grade 5 TEAE
- SAE
- Leading to discontinuation of PT2385

Summaries of the following TEAEs will be provided by system organ class and preferred term.

- All TEAEs
- TEAEs by maximum severity
- TEAEs grade 3 or higher
- PT2385 related TEAEs
- Grade 3 or higher PT2385 related TEAE
- Serious TEAEs
- TEAEs that led to permanent discontinuation of study of PT2385

A summary of the number of deaths within 30 days of administration of the last dose of study drug and deaths more than 30 days after administration of the last dose of study drug will be provided.

Listings will be provided of AEs identified as treatment-limiting toxicity, deaths, SAEs, and AEs leading to discontinuation of PT2385 tablet treatment.

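### SAE collection opens only at the first dose, so a serious event caused by a protocol-required screening procedure requires no 24-hour SAE report, even in screen failures

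*Combined protocol and SAP*

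**What the plan says.** **Reporting window.** Section 12.2.1.1 requires AEs to be reported "from the time of administration of the first dose of study drug until the final visit indicated in Appendix 1". Section 12.2.1.2 uses the same limits for AEs and SAEs: "from the time the first dose of study drug is administered until the final visit indicated in Appendix 1". In Appendix 1 the Adverse Events row is blank at Screening and is first marked at Week 1.

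**24-hour rule.** Section 12.7 sends any AE that meets the seriousness criteria to the sponsor's designee within 24 hours. It sets no start date of its own and has no rule for events caused by study procedures.

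**Where pre-dose findings go.**
- Section 12.6: "All conditions present before administration of the first dose of study drug should be documented as medical history".
- Section 13.3.6.1: "Adverse events occurring from the time the patient gives consent but prior to study drug administration will be captured on the Medical History CRF".
- Section 12.1.7 sends clinically significant laboratory abnormalities found at screening to medical history.
- Section 12.1.5, on physical examination, has an exception that the other three lack. Before the first dose, "any new or worsened abnormalities (other than those due to protocol required procedures) should be recorded as medical history".

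**Causality and IRB.** The scale in 12.4 rates the relationship of an event to PT2385 only. Section 14.5 makes the Principal Investigator responsible for telling the IRB about problems that put patients at risk.

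**The concern.** Once a patient has consented, procedures done because the protocol demands them are a risk that the trial imposes. If one of them causes serious harm, the sponsor should hear of it promptly and the record should show that the trial caused it. As written, the reporting clock starts at the first dose, after all screening procedures are over.

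The screening procedures are not trivial in this population. Appendix 1 and Section 10.1.1 call for CT, with or without contrast, or MRI; Section 13.3.4 describes contrast-enhanced CT. Appendix 4 adds baseline imaging of other organs, including brain and spine MRI for CNS hemangioblastomas. Pulse oximetry on exertion goes with the vital signs. Section 7.2.1 admits patients with serum creatinine up to 2.0 × ULN or a measured clearance of at least 30 mL/min.

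Two things are at stake. The sponsor may not learn of a serious procedure-related event in time to act on it. And harm caused by the trial may be filed as if it were part of the patient's own medical past.

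**Working it through.** The documents give no figure to reproduce, and the point rests on no sample size, rate or error probability. The check is a comparison of the sections, taking a serious event caused by a screening scan before the first dose.

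| Section | What it does with the event |
|---|---|
| 12.2.1.1 | Outside the AE window, which opens at the first dose |
| 12.2.1.2 | Outside the SAE window, same start |
| Appendix 1 | No AE collection marked at Screening (Day -28 to Day -1) |
| 12.7 | 24-hour report applies to serious AEs; adds no window from consent |
| 12.6 | Medical history, no exception for procedures |
| 13.3.6.1 | Medical History CRF, no exception for procedures |
| 12.1.7 | Laboratory abnormality goes to medical history, no exception |
| 12.1.5 | Examination finding due to a required procedure is excepted from medical history; no other place named |
| 12.4 | No category for relation to a study procedure |
| 14.5 | General duty to inform the IRB |

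1. *Is an SAE report required?* The event precedes the window in both 12.2.1.1 and 12.2.1.2. The definition in 12.2.1.2 points the same way, "An SAE is any AE occurring at any dose and regardless of causality that meets any of the following criteria", although its mention of dose is not decisive by itself. Section 12.7 depends on those definitions and does not widen them. No section requires the report.

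2. *Does later dosing bring the event in?* Only if it worsens. Section 12.6 says that conditions present before AE collection starts are not to be recorded as AEs, but a worsening or complication is. An injury that is stable or resolved by Day 1 stays outside.

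3. *What about screen failures?* They receive no dose, so the window never opens for them and they are not in the Safety Analysis Set (13.2). They do belong to the Enrolled Population, defined as screened and consented patients and used for data listings, so a medical-history entry could still be listed.

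4. *Is the event recorded at all?* Under 12.6, 12.1.7 and 13.3.6.1, yes, as medical history. Under 12.1.5, an examination finding caused by the procedure is left out of that instruction and given no other home. One section therefore conflicts with three broader ones.

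5. *Which text creates the gap?* Deleting the parenthesis in 12.1.5 would remove the recording conflict, but the SAE window would still open at the first dose. The gap comes from 12.2.1.1 and 12.2.1.2; 12.1.5 adds a separate contradiction about recording.

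**The case against.** The strongest reply is that starting collection at the first dose is a deliberate choice, applied consistently in 12.2.1.1, 12.2.1.2, 12.6, 13.3.6.1 and Appendix 1, and that pre-dose events are still captured as medical history. The consistency is real. It does not answer the point: the choice leaves harm imposed by the trial outside prompt reporting, and a Medical History entry carries neither a seriousness rule nor a deadline.

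It can also be argued that 12.7 covers any serious AE and that 13.3.6.1 itself calls pre-dose events adverse events, so the 24-hour rule might reach them. But that same sentence sends them to the Medical History CRF, and three other places fix the start at the first dose. At best a site would have to guess.

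The procedure risk should not be exaggerated. Histology is not required for entry, fresh tissue is taken only from patients who have tumors excised during the study, contrast is optional in 10.1.1 and Appendix 1, and imaging may overlap with usual surveillance in this disease (4.1.1, 4.2). All of that stands and limits how often the gap would matter.

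Four stronger readings go beyond the documents:
- *Such harm is recorded nowhere, or never reported.* Sections 12.6, 12.1.7 and 13.3.6.1 give it a place, 14.5 keeps the IRB duty, and an investigator may report voluntarily. What the text supports is that no SAE report is required.
- *The exception in 12.1.5 causes the gap.* It concerns physical examination findings, and may be meant only to spare sites from listing minor procedure marks.
- *A procedure-related change contaminates the laboratory baseline.* Section 13.3.6.2 does not say which pre-dose value is baseline, and reporting the event would change no laboratory value.
- *A probability of at least one missed SAE can be stated.* The documents give neither the number screened nor a rate of serious procedure-related events.

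**Conclusion.** The point holds as a gap in the safety-reporting rules. Because the AE and SAE window opens at the first dose, a serious event caused by a protocol-required screening procedure needs no 24-hour report to the sponsor. The scope is every consented patient for up to 28 days before dosing, and screen failures for the whole of their participation. The recording rules also conflict: 12.1.5 excepts procedure-related examination findings from medical history, while 12.6, 12.1.7 and 13.3.6.1 make no exception.

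The conclusion rests on reading 12.7 as bound by the window in 12.2.1.1 and 12.2.1.2, which is the natural reading. It needs no assumption about how often such events occur. They may well be rare, and no frequency is claimed here. The window also leaves out serious pre-dose events unrelated to any procedure; confining the recommendation to procedure-related events is a choice aimed at the risk that the trial itself imposes. The two-stage design, the primary analysis and the TEAE summaries are unaffected.

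**What to change.** 1. In 12.2.1.1, 12.2.1.2 and 12.7, state that between informed consent and the first dose, any AE attributed to a protocol-required procedure is recorded on the AE CRF and, if serious, reported within 24 hours, and that this applies to screen failures.
2. Reconcile 12.1.5, 12.1.7, 12.6 and 13.3.6.1 with that rule, so that only other pre-dose conditions and findings go to medical history. Including 12.1.7 matters, because otherwise a laboratory abnormality caused by a procedure would still be sent to medical history.
3. Mark Screening in the Adverse Events row of Appendix 1, with a footnote limiting it to procedure-related events.
4. Add an attribution to study procedure in 12.4, since the present scale covers PT2385 only.
5. In 13.3.6.1, list these events separately and state that they are not TEAEs.

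The cost is a few sentences across these sections, one CRF field, one listing, and possibly an occasional extra SAE report.
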